## Abstract/Summary of the research

Professional musicians are exposed to chronic high volume of continuous and repeated physical movements, sometimes in challenging and ergonomically unfavourable anatomical body positions, in order to acquire and improve technical playing skills. As a consequence, musicians are vulnerable to developing adverse playing-related musculoskeletal disorders (PRMDs) that may affect the manner in which and the extent to which music can be practised and performed.

In order to find out effective solutions for PRMDs and to develop future preventive measures, it is fundamental to firstly identify the main risk factors that play a significant role in the development of adverse musculoskeletal (MSK) conditions and symptoms.

The aim of the study will be to identify those factors associated with increased risk of PRMDs among music students. A further goal is to characterise and describe the clinical features of PRMDs, as well as determine the evolving course of PRMD's in music students during their professional training.

All pre-college and university-level students from several European music academies will receive an invitation to complete a web-based questionnaire survey at each of three occasions (baseline; 6-months follow-up; 12-months follow-up).

The web-based survey will include questions about any pain, PRMD and/or MSK problem they may have due to their musical practice, and different outcome measures (i.e. lifestyle and physical activity, practice habits, behaviour toward prevention and health history, level of stress, perfectionism, fatigue and disability).

To the best of our knowledge, no other longitudinal studies on risk factors for PRMDs have been conducted so far. Therefore, the study can be considered as an opportunity to fill the gaps of current research on PRMDs and generate new knowledge in educational and employment musical contexts.

# Background/Rationale of the project

It has been shown that professions with high physical demands and/or frequently repeated movements like computer use are associated with a higher prevalence of MSK problems (Roquelaure et al. 2006; Sim et al. 2006; Cote et al. 2008). Similarly, professional musicians are exposed to chronic high volume of continuous and repeated physical movements and are vulnerable to developing adverse MSK conditions and symptoms (Kok et al. 2013; Chan and Ackermann 2014), that may affect the manner in which and the extent to which music can be practised and performed (Kok et al. 2013; Chan and Ackermann 2014). Indeed, this phenomenon was described by Zaza et al. (1998) as playing-related musculoskeletal disorders (PRMDs) and includes "any pain, weakness, numbness, tingling, or other physical symptoms that affect a musicians' capacity to sing or to play their instruments at the level they are accustomed to". This definition does not include mild transient aches or pains. In fact, according to Zaza et al. (1998), musicians use the words mild, just, slightest, normal and little to describe such aches and pains that would not be considered to be related to PRMD, because they don't affect the ability to play the musical instrument and are considered as "normal" as every-day pain (Zaza et al. 1998).

Current literature suggests that PRMDs do not only occur when entering the professional world, but are already present at the very beginning of musicians' professional education. A study reported that 25% of music students at university level, admitted that they had suffered from PRMDs, before starting their degree course (Spahn et al. 2004). Other cross-sectional studies have indicated that 43% of university-level students of music experienced a health problem related with their activity as musicians during the early stages of their education (Zaza 1992). Brandfonbrener

(2009) reported a playing-related pain prevalence between 84% and 87% among first year music students at university level and found that the majority had already suffered from PRMDs as pre-college students or even younger. Moreover, it has been shown that at least 45% of university-level students of music seek help from clinical professionals during their training because of PRMDs (Spahn et al. 2004; Williamon and Thompson 2006).

In order to find effective solutions to prevent or minimise the development of PRMDs and consequences for music students, it is fundamental to firstly identify the main risk factors that contribute to the development of PRMDs.

Among the performing arts literature, the most reported common factors for the development of PRMDs in musicians include: type of instrument, muscle fatigue, the use of repetitive movements during long hours of practice, poor posture (body position demanded by the shape and weight of the instrument), poor physical condition, overuse, insufficient rest breaks, difficult repertoire, change of instrument and poor technique (Wynn Parry 2004; Guptill and Zaza 2010; Paarup et al. 2011; Ackermann et al. 2012).

Furthermore, several studies revealed that there were positive associations between developing a PRMD and psychological stressors (i.e. performance anxiety, depression, personality traits and stress) (Guptill et al. 2012; Kenny and Ackermann 2015; Berque et al. 2016).

In fact, music students have to be prepared to work in an environment with high psychological demands (Holst et al. 2012; Paarup et al. 2012), having to perform efficiently and effectively with an excellent preparation and a deep awareness of audiences' expectations (Wynn Parry 2004).

Moreover, the first year of a degree course in music is particularly demanding (Zander and Spahn 2006) and the transition between pre-college- and university-level requires intensified practice. This is indispensable primarily because students need to familiarise themselves with the higher instrumental performance demands of a different and more competitive psychosocial environment involving different approaches related to technique and performance, introduced by new professors and teachers. In fact, previous research showed that the first onset of psychological and physical symptoms among university-level students of music at early stages are strongly correlated with the increase of practice time (Fry 1987).

However, students can be trained by their teachers on how to improve technique and playing habits. For instance, mental practicing (i.e. without the instrument) can help diminish repetition and may increase the learning process (Bandura 1986).

A proper prevention and health awareness could be a potential contribution to psychosocial and physical factors in the performing art field (Chan and Ackermann 2014) and may address physical and psychological issues of health prevention. In fact, it has been frequently shown that a fundamental element in the prevention and management of MSK disorders is correct health education and medical advice (Silverstein and Clark 2004; Chan and Ackermann 2014).

Unfortunately, due to a lack of longitudinal studies, low methodological quality (i.e. high measurement bias, inappropriate statistical analysis) and large heterogeneity of assessment approaches and outcomes (Berque et al. 2016), currently available studies are capable of only offering a limited appraisal of possible relationships between the activity of musicians and the development of a PRMD.

The existing literature on risk factors among musicians cannot be considered acceptable in order to establish definitive links between the physical activity characteristics of musicians and their risks of developing PRMDs. This is because the available studies are predominantly cross-sectional, often based on a retrospective design and terms

such as prognostic facts or predictor are inappropriately used to indicate associations (Baadjou et al. 2016; Berque et al. 2016).

In fact, cross-sectional studies cannot be considered appropriate to research risk factors (Baadjou et al. 2016). In the interpretation of associations from cross-sectional studies, the direction of cause and effect it is extremely difficult to establish (Croft et al. 2001), because the presence of risk factors and the occurrence of an outcome (i.e. PRMDs) are assessed simultaneously. For example, anxiety or distress may be a risk factor for the development of PRMDs, but it is equally possible that PRMDs might contribute to increased anxiety or distress.

Currently, although there is a robust conceptual and physiological framework to expect a linkage between the physical activity characteristics of musicians and their risks of developing PRMDs, there is neither sufficient scientific evidence for this linkage nor the basis on which clinical prevention of PRMD can be developed (Rickert et al. 2015; Baadjou et al. 2016; Berque et al. 2016;).

Several recent studies and reviews strongly recommended developing a longitudinal study with a combination of biological, psychological and social potential factors that contribute to the development of PRMDs (Kaufman-Cohen and Ratzon 2011; Leaver et al. 2011; Kenny and Ackermann 2013; Rickert et al. 2015; Baadjou et al. 2016; Berque et al. 2016).

It is plausible that with more evidence relating to the modifiable factors that may increase the risk of adverse outcomes, targeted behaviour-modification and health-promotion might be ultimately designed to counteract the risk of developing PRMDs. Relevant targeted interventions could be implemented then either at the initiation of a career in music, or more effectively delivered as intermediate or ongoing intervention during, or in the transition towards, professional musicianship.

## Aims/objectives

The aim of the study will be to identify those factors associated with increased risk of PRMDs among music students. A further goal is to characterise this novel population of study and describe the clinical features of PRMDs, as well as determine the evolving course of PRMD's in music students during their professional training.

#### Research questions and hypotheses

Primary research question:

What are the main factors associated with increased risk of PRMDs in music students undertaking professional training?

Secondary research questions/objectives:

- 1. What is the prevalence of musculoskeletal disorders among university-level students in comparison with pre-college students?
- 2. Monitor and characterise the impact of the transition between pre-college and university-level music training on the development of PRMDs.
- 3. (Are there any differences in the severity and symptoms associated with PRMDs among music student groups at different levels of music training?)
- 4. Monitor and characterise the time course of PRMD development

- 5. (Are there significant differences in PRMD incidence between university-level students and pre-college students?
- 6. During training, do music students develop any type of musculoskeletal disorder that doesn't affect their ability to play at the level to which they are accustomed to?
- 7. Characterise health related quality of life and outcomes in music students at different stages of professional training.

Considering the aims and the research questions of the programme, the following hypotheses are formulated:

H1: The development of PRMDs is associated with a multitude of risk factors (i.e. age, gender, number of hours of practice, previous history of injury, poor physical status, psychological stress, perfectionism, fatigue) among music students.

H2: There is a higher prevalence of PRMDs among university-level students in comparison with precollege students.

H3: There is a higher prevalence of PRMDs among university-level students in the early stages of their training (transition between university-level and pre-college).

H4: University-level students develop more PRMDs over the years of their training than pre-college students.

H5: During their training, music students of both levels develop MSK disorders that affect their ability to play at the level they are accustomed to.

H6: Health and quality of life among music students is progressively poorer over the years of training (from the last two years of pre-college to the last years of Master-level)

# Methodology

#### Study Design

This prospective longitudinal cohort study will be conducted through the following three phases (Figure 1):

- (1) A baseline cross-sectional survey to characterise the study population and subgroups, and form the basis for the evaluation of associated factors and relationships with the development of PRMDs;
- (2) A 6-months follow-up survey, and
- (3) A 12-months follow-up survey.

[figure not shown]

Figure 1 Research planning chart including main features of the cohort study

The study protocol has been approved by the Research Ethics Panel of the Queen Margaret University, Edinburgh (REP 0177).

After the first baseline data collection (Phase 1), the cohort of students will be broken down into:

- Cohort 1: music students (both pre-college and university-level) who are free of pain, PRMDs and/or MSK problems at baseline data collection
- Cohort 2: music students (both pre-college and university-level) who aren't free of pain, PRMDs and/or MSK problems at baseline data collection

Afterwards, the two cohorts will be followed and invited for reassessment at 6 months (Phase 2) and 12 months (Phase 3).

The 6-months and 12-months follow-ups for the Cohort 1 will be essential to monitor and record the development of new incidents of invasive pain, PRMDs and/or MSK problems within a period of a year and to enable characterisation of the nature and time course of developing pain, PRMDs and/or MSK problems.

The analysis of the results will attempt to answer primary research question and secondary research question 3 and 4, addressing the lack of any similar type of data in the current literature.

Similarly, the follow-ups for the Cohort 2 will be important in order to characterise the impact and time course of changes in any pain, PRMD and/or MSK problem within a 12-month period.

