# The web-based survey

The web-based survey will include different outcome measures, which have been selected according to the relevant findings of previous cross-sectional studies and systematic reviews among the performing arts literature (Figure 2).

Each outcome measure correspond to a suspected factor that may be associated with the development of PRMDs.

The survey will start with questions about personal background and lifestyle (i.e. age, gender, self-reported weight and height, nationality, smoking status and sleeping habits), as well as practice habits (i.e. number of

hours of practice and years of experience) health history (i.e. major past injuries/accident/disorders and current medication) and health status (Self-Related Health - SRH).

Afterwards, in order to divide the cohorts, the presence of pain and/or MSK problems will be assessed through the following question: "When did you last experience a bout of significant pain and/or musculoskeletal problem?" with the following list of possible answers:

- 1. I currently have pain and/or a musculoskeletal problem (up to one month)
- 2. 2-3 months ago
- 3. 4-6 months ago
- 4. Up to 12 months ago
- 5. More than 12 months ago
- 6. I have never had any pain and/or musculoskeletal problem

[figure not shown]

Figure 2 Procedure of the web-based survey

According to the answer to this question, students will be addressed to different web pages throughout the survey (Figure 2):

- Respondents with a current pain and/or MSK problem (up to one month) will be asked questions to describe their current pain, to report their disability with Pain Disability Index (PDI), the Performing Arts

Section of Quick Disabilities of the Arm, Shoulder and Hand Outcome Measure (PAS –Quick DASH) and their pain self-efficacy with 2-item short form of the Pain Self-efficacy Questionnaire (PSEQ-2), as well as the Nordic Musculoskeletal Questionnaire (NMQ) for the assessment of musculoskeletal pain in the last 12 months

- Respondents without a current pain and/or MSK problem but a positive history of pain and/or MSK problem in the last 12 months (2-3 months ago, 4-6 months ago or up to 12 months ago) will be asked to answer the NMQ and questions on pain management to investigate how their pain and/or MSK problem has been treated
- Respondents without pain or with pain and/or MSK more than 12 months ago will be directly addressed to the next section

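### About one problem-free month seems enough to enter Cohort 1, so its new incidents mix recurrences with new onsets to an unknown extent, and the stated analysis does not separate them

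*Protocol*

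**What the plan says.** Under Study Design, Cohort 1 consists of students "who are free of pain, PRMDs and/or MSK problems at baseline data collection" and Cohort 2 of all others. No third group is named. Both are followed: "the two cohorts will be followed and invited for reassessment at 6 months (Phase 2) and 12 months (Phase 3". Follow-up of Cohort 1 is meant to "monitor and record the development of new incidents of invasive pain, PRMDs and/or MSK problems within a period of a year". On the use of these data the section states: "The analysis of the results will attempt to answer primary research question and secondary research question 3 and 4".

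Under The web-based survey, one item on the date of the last significant bout is introduced thus: "in order to divide the cohorts, the presence of pain and/or MSK problems will be assessed through the following question". Its first answer reads "I currently have pain and/or a musculoskeletal problem (up to one month". The other answers place the last bout 2-3 months ago, 4-6 months ago, up to 12 months ago, more than 12 months ago, or never. The survey has a separate route for "Respondents without a current pain and/or MSK problem but a positive history of pain and/or MSK problem in the last 12 months", but that route is not linked to a cohort.

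The Data analysis section adjusts the logistic regression for age, gender and instrument. Its predictors for incidence are gender, instrument group, age, years of playing, hours of practice and questionnaire scores. Time since last bout is not among them. Nor is previous injury, although H1 names it as a risk factor.

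**The concern.** A risk-factor cohort needs a defined population at risk and a defined event. Here the risk set appears to require only about a month without a problem, and no rule says when a bout in follow-up is new rather than the return of a recent one.

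Three consequences are possible.

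- Recorded incidence describes a blend of two risks, in proportions that depend on who happened to enrol.
- A factor that acts mainly on onset has its risk ratio pulled towards 1 by recurrences that it does not drive.
- Baseline distress or fatigue may be the residue of a bout two or three months earlier. If that student then has another bout, the score appears to have preceded a new problem. The Background section rejects cross-sectional evidence because distress may be either cause or effect of PRMDs. A short window leaves part of that ambiguity in place.

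The primary question is the one most exposed, because the protocol assigns it to this follow-up.

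**Working it through.** **Step 1: who enters Cohort 1.** Study Design divides students in two by their state at baseline. The dividing item has one answer for a current problem, reaching back one month. The survey text describes those with a bout 2 to 12 months ago as having no current problem. With only two cohorts, they fall into Cohort 1. This mapping is inferred, since the text never assigns the six answers to cohorts outright.

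**Step 2: how much mixing.** The plan states no rate that could be reproduced. Let p be the share of Cohort 1 with a recent bout, r their 12-month risk of another, and i the 12-month risk in the rest. All values below are assumptions.

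- Recorded incidence = p·r + (1−p)·i
- Recurrence share = p·r / [p·r + (1−p)·i]

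Example with p = 0.25, r = 0.40, i = 0.20: incidence = 0.10 + 0.15 = 0.25, and recurrence share = 0.10/0.25 = 40%.

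| p | r 0.30, i 0.30 | r 0.40, i 0.20 | r 0.50, i 0.15 | r 0.60, i 0.10 |
|---|---|---|---|---|
| 0.10 | 10% | 18% | 27% | 40% |
| 0.25 | 25% | 40% | 53% | 67% |
| 0.43 | 43% | 60% | 72% | 82% |
| 0.60 | 60% | 75% | 83% | 90% |

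Recurrences are the majority only if p exceeds i/(r+i), which is 0.50, 0.33, 0.23 and 0.14 across the four columns. Recorded incidence is 1.00 to 2.25 times i at p = 0.25 and 1.00 to 3.15 times i at p = 0.43. It exceeds i only when r is greater than i.

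**Step 3: dilution of a risk ratio.** Assume i = 0.15, r = 0.40, and a factor equally common in both groups that doubles onset risk and leaves recurrence unchanged.

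Pooled RR = [p·0.40 + (1−p)·0.30] / [p·0.40 + (1−p)·0.15]

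- p = 0.43: 0.343/0.2575 = 1.33
- p = 0.60: 0.360/0.300 = 1.20
- p = 0.77: 0.377/0.3425 = 1.10

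The outer values of p come from assuming that 30% have a current problem and that 12-month prevalence is 60% or 84%: (0.60−0.30)/0.70 = 0.43 and (0.84−0.30)/0.70 = 0.77. The 84% is a cited first-year figure in the Background, given without a time window. The 60% and 30% are pure assumptions.

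Dilution does not need r to exceed i. With both at 0.15 and p = 0.43, pooled RR = 0.43·1 + 0.57·2 = 1.57. If the factor also doubles recurrence, pooled RR is 2.0 and nothing is lost.

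**Step 4: comparison by level of training.** Keep r and i the same at both levels, so that true onset does not differ, and vary only p across the four (r, i) pairs of step 2.

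- p 0.25 pre-college, 0.43 university: RR 1.00 to 1.40
- p 0.25 pre-college, 0.60 university: RR 1.00 to 1.78
- p 0.60 pre-college, 0.43 university: RR 0.79 to 1.00

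The distortion can run in either direction, and it vanishes if p is equal at both levels or r equals i.

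**The case against.** The plan speaks of new incidents and never promises first-ever onset. Counting new episodes among people free of a problem at baseline is a recognised target, and H1 lists previous injury as a risk factor, so students with a history are meant to be in the risk set. This stands as far as it goes: including them is not the error. But a target that includes them still needs a definition of new and an analysis that uses the history, and the listed predictors omit it.

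The item asks about any significant pain or musculoskeletal problem, not about PRMDs or a body site. A later bout elsewhere need not be a recurrence. Conversely, a last bout more than 12 months ago is still a history. Both points stand, so neither group below is pure.

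The dilution example is an extreme case, since nothing in the protocol says that any factor leaves recurrence untouched. That is fair, and it is offered only as an illustration.

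The design and survey figures are not shown in the copy reviewed and may settle the mapping of answers to cohorts. An analysis plan, also not shown, may add stratification. The definition of the cohort and its event nevertheless belongs in the protocol.

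A reader might infer that most Cohort 1 incidents are recurrences. The documents do not support that: they give no rates for students who are problem-free at baseline, and the background percentages describe all students. A reader might also infer that H4, "University-level students develop more PRMDs over the years of their training than pre-college students", could be met by recurrence alone. The text does not tie H4 to Cohort 1 incidence: Study procedure assigns secondary question 5, incidence by level, to the baseline phase. No passage shows that recent history is commoner at university level.

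**Conclusion.** The point holds in a limited form. On the plain reading, about a month without a problem suffices for Cohort 1, bouts that follow one 2 to 12 months earlier count as new, and the stated analysis neither separates nor adjusts for them. Cohort 1 incidence and the risk ratios for the primary question may be biased, and baseline distress or fatigue may partly reflect a recent bout. The size cannot be fixed from the documents. The recurrence shares of 10% to 90%, and the pooled risk ratios of 1.10 to 1.57 for a factor that doubles onset only, rest wholly on assumed rates. Any comparison of Cohort 1 incidence by level could be distorted upwards, downwards or not at all. The conclusion also depends on the inferred mapping of answers to cohorts. It should be corrected, because it concerns the primary question and the remedy uses data already planned.

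**What to change.** 1. State which of the six answers place a student in Cohort 1, and define a new incident, including the episode-free period it requires.
2. Report Cohort 1 incidence and risk ratios separately for (a) last bout more than 12 months ago or never, labelled as a new episode after at least 12 problem-free months and not as first-ever onset, and (b) last bout 2 to 12 months ago, labelled as likely recurrence.
3. Include time since last bout as a covariate in the pooled regression, and show the pooled result beside the two strata. The covariate addresses confounding by recent history. It does not reveal a factor whose effect differs between onset and recurrence, so the strata are needed as well.
4. If incidence is compared by level of training in Cohort 1, make the comparison within these strata.

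No new data are needed, only wording in Study Design and Data analysis. The price is precision. At an assumed 43% with a recent bout, and similar risks in both groups, intervals on the log scale widen by about 1/√0.57 = 1.32 in stratum (a) and 1/√0.43 = 1.52 in stratum (b).
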